## 5.0 STUDY PROCEDURES

Table 2 provides an overview of the evaluations to be performed at each study visit/follow-up. See also Figure 1, the study flow diagram, for details on timing of these evaluations.

**Table 2. Schedule of Evaluations and Visits**

	Screening	Baseline	Follow-Up Phone Calls		
	Visits 1a-1b	Visit 1c	Visit 2	Visit 3	Visit 4
			Month 1	Month 3	Month 6
		Cardioversion			
Initial inclusion/exclusion evaluation	X				
Screen for coffee consumption habits	X				
Screen for significant other caffeinated product consumption	X				
Informed consent	X				
Demographics		X			
Height and weight		X			
Detailed history of coffee consumption habits		X	X	X	X
Detailed history of alcohol consumption habits		X	X	X	X
Detailed medical history		X	X	X	X
Targeted medication history		X	X	X	X
Assessment of clinically available pre-cardioversion ECG		X			
Assessment of clinically available post-cardioversion ECG		X			
Randomization		X			
Detailed history of other caffeinated product consumption			X	X	X
AF symptoms			X	X	X
Assessment of AliveCor KardiaMobile or Apple Watch ECG strip			X	X	X
Assessment of clinically available ECG or ambulatory			X	X	X

ECG monitoring from physician/healthcare provider					
Adverse events/serious adverse events evaluation			X	X	X
Targeted medical care utilization			X	X	X
Vital status			X	X	X

### 5.1 Screening for Inclusion/Exclusion Criteria

Each potential participant's medical record will be briefly reviewed for available inclusion and exclusion criteria data. Potentially eligible patients will be subsequently approached to ascertain interest and coffee/other caffeinated product consumption. After informed consent is obtained, pre- and post-cardioversion ECGs will be assessed to record AF and sinus (or other appropriate non-AF underlying) rhythm respectively. Once this is confirmed, randomization will be undertaken.

### 5.5 Electrocardiogram (ECG)

Pre- and post-cardioversion electrocardiogram (ECG) data will be assessed at baseline. Results from the ECG test will be entered onto the case report form (CRF).

### 5.6 Physical Examination and Medical History

The screening evaluation will collect medical history data for assessment of inclusion/exclusion criteria, including coffee/other caffeinated product consumption history.

### 5.7 Targeted Medication Inventory

Current/regular use (since the last study follow up) of a specific list of concomitant medications/therapies will be documented at baseline (post cardioversion) and at all follow-up visits. Medication data will be collected by self-report and electronic medical record on a CRF and will include type of medication. The list of targeted medications/therapies includes AF-related medications (e.g., anticoagulants, antiarrhythmics, negative chronotropic agents).

### 5.8. Specific Adverse Events

Site personnel will review medical records to determine if any of the prespecified AEs occur:

1. Any death
2. Myocardial infarction
3. Stroke/transient ischemic attack
4. Heart failure exacerbation
5. Hospitalization
6. Syncope
7. Emergency Room Visit

## 6.0 Risks and Benefits of the Study

## **6.1 Cardioversion Procedure**

The cardioversion procedure involves several risks, but each of these participants would experience these risks whether or not they choose to participate in DECAF or not, since inclusion is this trial requires already having a planned/scheduled cardioversion procedure. The known risks have been shown to occur in less than 1% of cases and include adverse reaction from administered medications for sedation/anesthesia, lack of success, induction of another arrhythmia, skin burn, or stroke or transient ischemic attack. Potential benefits of cardioversion include reduction in symptoms (such as palpitations, shortness of breath, and dizzy spells), improvement in energy/well-being, and strengthening of heart function (if AF is a major cause or contributor to weakened function).

## **6.2 Coffee Abstinence or Continuation**

Abstinence from coffee and other caffeine-related products may result in caffeine-withdrawal, symptoms of which can include headache, fatigue, anxiety, difficulty concentrating, depressed mood, irritability, tremors, and low energy. It is not clear what effect, if any, coffee has on AF and AF recurrence; this forms the rationale for the present study. Potential benefits of coffee abstention may therefore include a reduction in AF recurrence. Conversely, it may be possible that coffee consumption is beneficial and abstinence may result in a greater likelihood of AF recurrence.

## **7.0 STUDY ROLES**

The DECAF study has been developed by the Principal Investigator at the University of California, San Francisco (UCSF). The study investigators are committed to conducting this study in a uniform manner, adhering to the study protocol and the operations manual. Standardization, supervision, and coordination of all procedures will be enhanced through peer review and quality control mechanisms.

### **7.1 Administrative Organization**

DECAF is organized and conducted by the coordinating center, the University of California San Francisco (UCSF) under the guidance of the Principal Investigator.

### **7.2 Enrolling Clinical Site**

The study will be conducted at 3 sites.

The Coordinating Center for DECAF will be at the University of California, San Francisco. Another site is University of Adelaide, Adelaide, Australia. The final site is Sunnybrook Health Sciences Centre, Toronto, Canada.

#### **7.2.1 Clinical Site Principal Investigator**

This study protocol will be conducted by the Principal Investigator and his staff. The Principal Investigator has experience in and will be responsible for:

- Conducting the study protocol in accordance with the signed agreement with the UCSF, the study protocol, all applicable FDA regulations (21 CFR Parts 50, 54, 56, 812), GCP guidelines, and any conditions of approval imposed by the IRB
- Providing IRB Approval and an Approved Informed Consent
- Screening and selecting appropriate participants
- Collection and archiving of data obtained pursuant to the requirements of the study protocol during the course of the study and after the study has been completed

It is acceptable for the Principal Investigator to delegate one or more of the above functions to an associate or co-Investigator, however, the Principal Investigator remains responsible for the proper conduct of the study protocol, complying with the study protocol, and collecting all required data.

## **8.0 PROTOCOL DEVIATIONS**

Principal Investigators are required to adhere to the study protocol, applicable federal (national) or state/local, laws and regulations, and any conditions required by the IRB or applicable regulatory authorities.

A protocol deviation is used to describe situations in which the clinical protocol was not followed. All major deviations from the study protocol will be reported, as soon as possible, but no later than 10 working days of notification of the event. In addition, all major deviations will be reported to the UCSF CC, as well as the local IRB as appropriate, per the IRB's reporting requirements.

## **9.0 QUALITY ASSURANCE AND DATA MANAGEMENT**

### **9.1 Clinical Site Investigator and Coordinator Training**

Each investigator and coordinator will be trained on the study protocol and procedures to ensure accurate and consistent study methods are used study-wide and throughout the entire study duration. Trainings will include review of the protocol, operations manual, CRFs, event reporting, and data management procedures.

### **9.2 Data Handling and Confidentiality**

Information about study participants will be kept confidential and managed according to the requirements of the Health Insurance Portability and Accountability Act of 1996 (HIPAA). Those regulations require a signed patient authorization informing the patient of the following:

- What protected health information (PHI) will be collected from study participants
- Who will have access to that information and why
- Who will use or disclose that information
- The rights of a research participant to revoke their authorization for use of their PHI

In the event that a participant revokes authorization to collect or use PHI, the Principal Investigator, by regulation, retains the ability to use all information collected prior to the revocation of participant authorization. For participants that have revoked authorization to collect or use PHI, attempts should be made to obtain permission to collect at least vital status (i.e., that the participant is alive) at the end of their scheduled study follow-up.

### **9.3 Source Documents**

Complete study files will be kept in a secure location. Participant files will include archives of completed CRFs and source documents. The CRFs are the primary data collection instrument for the study and are considered source documents. All data requested on the CRF will be recorded. Source data also include original records of clinical findings, observations, or study measurement results (e.g., hospital records, clinical and office charts, laboratory notes, dispensing records, recorded data from automated instruments, and patient files).

### **9.4 Data Collection and Management**

The data will be compiled into the central study database at UCSF. Sites will collect and enter study data onto electronic CRFs via the online study database, REDCap. The study data will be stored in the study database at UCSF and will be subjected to checks for completeness, consistency and validity. Data entry will occur in a timely manner.

For all procedures, clinical site personnel will only have access to their own site data.

## 9.5 Data Monitoring

[The investigators] will be responsible for monitoring procedures related to study conduct and data collection/reporting to ensure the quality and integrity of the study data. A representative will check the completeness of participant study records, the accuracy of entries on the CRFs, the adherence to the protocol and to Good Clinical Practice, as per the DECAF Monitoring Guidelines.

To ensure data quality, we will perform the following Quality Assurance procedures: after the first two participants are randomized and the study intervention is performed, 100% of inclusion/exclusion criteria and key baseline data points will be reviewed against source documentation collected from the site (such as the participant's de-identified initial EP H&P, procedure note and first follow-up EP note). In addition, specified de-identified documentation will be requested from each site to perform source verification on a random 10% sample of key study data. If during the course of the study the error rate exceeds a 5% threshold, the percentage of source verification will increase until control is demonstrated.

## 10.0 STATISTICAL METHODS

### 10.1 Sample Size and Randomization

The goal of this trial is the enroll a total of 200 participants (n=100 per treatment group).

Assuming a 0.05 two-tailed alpha level, 1:1 randomization scheme, 50% recurrence rate in the absence of coffee, and potential 10% loss to follow-up, a sample size of n=200 (100 per arm) will provide approximately 80% power to detect a 1.63 times increased hazard of AF recurrence between the groups.

The table below summarizes the minimum detectable relative hazards in Cox models with binary predictor, by baseline AF recurrence rate (RR) (rows) and Percent Lost to Follow up (LTFU) (columns)

	5% LTFU	10% LTFU
50% RR	1.68	1.69
60% RR	1.62	1.63

Randomization will be performed 1:1 with stratification across sites.

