### **5.0 SAMPLE SIZE AND POWER CALCULATIONS**

The goal is to enroll a total of 200 participants (n=100 per treatment group) study-wide.

The sample size is based on the following assumptions: (1) a 50% incidence of AF recurrence; (2) 10% loss to follow-up; and (3) 0.05 two-tailed alpha level. Under these assumptions, a sample of 200 individuals randomized 1:1 to either coffee abstention or continued caffeinated coffee consumption will provide 80% power to detect a 1.63 times increased hazard of AF between the groups.

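### At the stated 50% recurrence and 10% loss, 200 participants give about 74% power for a hazard ratio of 1.63, not 80%; the protocol's own table gives 1.69 for those inputs

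*Combined protocol and SAP*

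**What the plan says.** Protocol 10.1 begins its inputs with "Assuming a 0.05 two-tailed alpha level, 1:1 randomization scheme" and continues with "50% recurrence rate in the absence of coffee, and potential 10% loss to follow-up". For 100 participants per arm it concludes that the trial "will provide approximately 80% power to detect a 1.63 times increased hazard of AF recurrence between the groups".

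A table follows, described as giving "minimum detectable relative hazards in Cox models with binary predictor", by recurrence rate and percentage lost:

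| Recurrence | 5% lost | 10% lost |
|---|---|---|
| 50% | 1.68 | 1.69 |
| 60% | 1.62 | 1.63 |

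SAP 5.0 has no table. It lists its assumptions as "1) a 50% incidence of AF recurrence; (2) 10% loss to follow-up; and (3) 0.05 two-tailed alpha level" and concludes that 200 participants "will provide 80% power to detect a 1.63 times increased hazard of AF between the groups". It does not say which arm the 50% describes.

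**The concern.** The sentence combines the 50% row's recurrence rate with the 60% row's hazard ratio. Both cannot be right at 80% power. If 50% was the planning rate, the detectable effect is understated and the power for 1.63 is overstated. If 60% was the planning rate, the assumption printed in both documents is wrong.

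This sentence is the worded justification for 200 participants. The SAP repeats it without the table that would expose the mismatch. Anyone using it to judge how large an effect a null or borderline result could have missed would start from the wrong figure.

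**Working it through.** **Inputs.** Two-sided alpha 0.05, 1:1 allocation, 100 per arm, 50% recurrence in the abstinence arm and 10% loss (Protocol 10.1). Follow-up is six months with censoring at withdrawal or month 6 (SAP 6.1). Two assumptions are added because the documents do not state them: constant hazards, and loss spread over follow-up.

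**Formulas.** Take six months as one time unit.

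- Recurrence hazard in the abstinence arm: λ = −ln(1 − p). In the coffee arm: λ × HR.
- Loss hazard: γ = −ln(1 − loss).
- Expected events in an arm with recurrence hazard h: 100 × h/(h + γ) × (1 − exp(−(h + γ))).
- Schoenfeld events for 80% power: D = 4(1.960 + 0.842)² / (ln HR)².
- Power with D events: Φ(ln HR × √D / 2 − 1.960).

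**Step 1: reproduce the table.** Solving for the hazard ratio that gives 80% power:

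| Recurrence, loss | Calculated | Protocol table |
|---|---|---|
| 50%, 5% | 1.681 | 1.68 |
| 50%, 10% | 1.690 | 1.69 |
| 60%, 5% | 1.621 | 1.62 |
| 60%, 10% | 1.629 | 1.63 |

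All four cells agree to two decimals, so the added assumptions are consistent with how the table was made.

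**Step 2: events needed.** For 1.63, ln HR = 0.4886 and D = 131.5, or 132 events. For 1.69, ln HR = 0.5247 and D = 114.0.

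**Step 3: events expected at 50% and 10%, with HR 1.63.** γ = 0.1054.

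- Abstinence arm: λ = 0.6931, giving about 47.7 events.
- Coffee arm: 0.6931 × 1.63 = 1.1298, giving about 64.9 events.
- Total: 112.6 events.

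**Step 4: power for 1.63.** Φ(0.4886 × √112.6 / 2 − 1.960) = Φ(0.632), or about 73.7%. A log-rank simulation with 8,000 runs per scenario gave 73.5% to 73.8% with loss spread over follow-up.

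**Step 5: check from the table alone.** If 1.69 has 80% power, power for 1.63 is Φ(2.802 × 0.4886/0.5247 − 1.960) = Φ(0.649) = 74.2%. This needs no model for hazards or loss.

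**Step 6: where 1.63 does reach 80%.** At 60% recurrence and 10% loss, 131.9 events are expected and power is 80.1%.

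**Step 7: sensitivity to the loss model at 50% recurrence.**

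- Lost participants contribute nothing: 90 × (0.5 + 0.6769) = 105.9 events, power 71.0%.
- Loss ignored: 100 × (0.5 + 0.6769) = 117.7 events, power 75.5%.
- Freedman's formula in place of Schoenfeld's, with loss as in Step 3: power 72.0%.

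**Step 8: the SAP's unassigned 50%.** If 50% is read as incidence over both arms combined, there are 100 events before loss and about 96 after it. Power for 1.63 is then about 67% and the detectable hazard ratio is 1.77. This reading does not reproduce the table.

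**The case against.** **Which figure is the slip is not shown.** Reproducing the table shows that it is internally correct. It does not show which row the trial was planned on. If 60% was intended, 1.63 and 80% are right and the printed 50% is the error. This stands. The SAP's repetition of 50% is some evidence for that rate, but it may be copied text. Either way, the sentence as written is wrong.

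**The correct figure is already on the page.** A protocol reader can find 1.69 one line below, and a null result would be judged mainly from the estimate and 95% confidence interval promised in SAP 6.1. This limits the consequence for protocol readers. It does not help someone reading SAP 5.0 alone.

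**The gap is small and changes nothing in the design.** Sample size, alpha, allocation, endpoint and the Cox analysis are unaffected, and there is no interim analysis. That is correct, and it is why the remedy is only textual.

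**The 74% depends on a model.** It does, within 71% to 75.5% across the loss models in Step 7. The mismatch with the table depends on no model. The routes found to 80% or more each contradict a stated input: a one-sided test (about 83% with loss as in Step 3), or treating 1.63 as a risk ratio with no loss (131.5 events, 80.0%).

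**The SAP's 50% is shorthand.** Protocol 10.1 already ties the rate to the absence of coffee, so the 67% and 1.77 figures describe a possible misreading of the SAP and not the likely design. That is fair; they support a wording clarification only.

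**Conclusion.** The power statement in Protocol 10.1 and SAP 5.0 is wrong as written. With 50% recurrence in the abstinence arm, 10% loss, 100 per arm and two-sided alpha 0.05, power for a hazard ratio of 1.63 is about 74%, some 6 points below the claim. The hazard ratio detectable with 80% power is 1.69. In terms of abstinence against coffee these are 1/1.63 = 0.61 and 1/1.69 = 0.59.

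The power figure rests on constant hazards and loss spread over follow-up, assumptions that reproduce every table cell. No way of handling the loss that was tried at the stated inputs brings it to 80%. The error is modest and leaves the design and analysis intact, but it is in the headline figure of both documents and should be corrected.

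**What to change.** The sponsor should confirm the intended planning rate and make the same correction in Protocol 10.1 and SAP 5.0:

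- If 50% was intended, replace 1.63 with 1.69 at 80% power, or keep 1.63 and state about 74% power.
- If 60% was intended, keep 1.63 and 80% and change the assumed recurrence to 60%.

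In either case, SAP 5.0 should say that the rate is the recurrence in the coffee-abstinence arm.

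The cost is one figure in each document and a short clarification in the SAP. If 50% stands, the declared sensitivity is slightly less favourable; if 60% is adopted, the plan rests on a higher assumed event rate. Enrolment and the analysis do not change.

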### 10.2 Intention-to-Treat (ITT)

The main intention-to-treat (ITT) analysis set will include all randomized participants, whether or not they are compliant with the treatment allocation for this trial. Every attempt will be made to collect data until the end of the follow-up period for all randomized participants and these data will be included as part of the main ITT analysis. The analyses for the primary objective will be performed using the ITT dataset.

Although substantial crossover is not anticipated, as treated and per protocol analyses will also be conducted if failure to comply with allocated treatment assignments occurs in more than 10% of cases or if there is a significantly different proportion of assignment adherence in one group compared to the other.

## 11.0 PUBLICATION

Any presentation/publication of any data from this study must be approved by the Principal Investigator prior to release.

## **12.0 ETHICAL CONSIDERATIONS**

This study is to be conducted according to US and international standards of Good Clinical Practice (FDA Title 21 part 812 and International Conference on Harmonization guidelines), applicable government regulations, and Institutional research policies and procedures.

### **12.1 Institutional Review Board (IRB) and Ethics Committee (EC) Approval**

This protocol and any amendments will be submitted to a properly constituted independent IRB for each clinical site, in agreement with local legal prescriptions, for formal approval of the study conduct. The decision of the IRB concerning the conduct of the study will be made in writing to the Principal Investigator. The Principal Investigator at each site should also provide a list of IRB members and their affiliates to the UCSF CC.

### **12.2 Informed Consent**

The investigator and/or study coordinator must explain to each participant the nature of the study, its purpose, the procedures involved, the expected duration, the potential risks and benefits involved, and any discomfort it may entail. Each participant must be informed that participation in the study is voluntary and that he/she may withdraw from the study at any time and that withdrawal of consent will not affect his/her subsequent medical treatment or relationship with the treating physician.

This informed consent should be given by means of a standard written statement, written in non-technical language. The subject should read and consider the statement before signing and dating it, and should be given a copy of the signed document. If the participant cannot read or sign the document, oral presentation may be made or signature given by the participant's legally appointed representative, if witnessed by a person not involved in the study, mentioning that the participant could not read or sign the documents. No participant can enter the study before his/her informed consent has been obtained.

The informed consent form must be submitted by the investigator for IRB approval. An informed consent template will be provided to all of the clinical sites for their use. Any changes to the template consent form suggested by the Investigator must be agreed to by the UCSF CC before submission to the local IRB, and a copy of the approved version must be provided to UCSF CC after IRB approval.

### **12.3 Declaration of Helsinki**

The investigator must conduct the trial in accordance with the Declaration of Helsinki.

**SUMMARY OF PROTOCOL CHANGES**

Protocol Date	Description of Change	Brief Rationale
Sept 5, 2021	Original version	N/A
Oct 19, 2021	Study duration changed from 12 to 6 months	To facilitate recruitment given frequent reluctance of patients to abstain from coffee
	Addition of Month-1 follow-up visit	To add an earlier timepoint than Month-3 given reduction in study duration to 6 months
	Amendment of inclusion criteria: "sustained AF or atrial flutter (provided patient has a history of AF)"	Given previous lack of reference to atrial flutter, to clarify that patients in flutter at time of cardioversion were eligible if they also had a history of AF
	Amendment of exclusion criteria: "recent/planned AF ablation within 6 months"	Previously was 12 months - change to reflect reduction in study duration to 6 months
	Correction of remaining references to previous study title to "DECAF" throughout document	Completion of prior change not undertaken throughout document in some places
January 19, 2023	Addition of second site: University of Adelaide	To facilitate recruitment
	Clarification of primary objective: "time to first confirmed AF recurrence and/or Aflutter recurrence following cardioversion"	Given previous lack of reference of atrial flutter, to clarify that either recurrent AF or flutter would fulfil primary endpoint
October 9, 2023	Addition of previously approved Month-1 follow-up visit throughout document where missing	Completion of prior change not undertaken throughout document in some places
	Addition of option to call & enroll patients remotely within 1 week of cardioversion if clinical care did not allow time for coordinator to approach during hospital visit	To facilitate recruitment as busy clinical care settings were preventing many eligible patients being approached by coordinators before cardioversion
	Amendment of exclusion criteria: "recent/planned AF ablation within 3 months"	Previously was 6 months - to facilitate recruitment as many otherwise eligible patients had had ablation within 6 months
May 31, 2024	Addition of third site: Sunnybrook Health Sciences Centre	To facilitate recruitment
	Amendment of secondary objectives: removal of AF and coffee abstinence symptom assessments	These secondary assessments were initially planned at the time of initial study design but due to practical constraints were not collected
	Amendment of inclusion criteria: "life expectancy of at least 6 months"	Previously was 1 year – change to reflect prior reduction in study duration to 6 months
	Amendment of "Lost to Follow-Up" procedure: clarified that medical record review was also utilized in addition to physician/healthcare professional contact to confirm AF recurrence status	Clarification that, in addition to contacting physician/healthcare professional, medical record use was approved to confirm AF recurrence status if patient did not attend follow up visits
	Removal of SF-36, hrQOL, and physical activity questionnaires	These assessments were initially planned at the time of initial study design but due to practical constraints these data were not collected
	Removal of Section 5.9 Targeted Medical Care Utilization	The collection of these data are already described in Section 5.10 Adverse Event Collection
	Amendment of Section 5.7 Targeted Medication Inventory: reference to dosage and frequency removed	Clarified that medication type was collected but not dosage or frequency

June 12, 2025	Clarification of primary objective: "time to first confirmed clinical recurrence of AF recurrence and/or atrial flutter recurrence, or device-detected recurrence lasting longer than 30 seconds" –	Given previous lack reference to device-detected recurrence, to clarify that device data was also reviewed and a threshold of 30 seconds utilized
	Amendment of secondary objectives: addition of adverse events and separate AF/atrial flutter assessment, and removal of other arrhythmia assessment	Clarification that adverse events and assessment of AF and atrial flutter recurrence separately are prespecified secondary endpoints, and that collection of other arrhythmias was not systematically undertaken due to practical constraints and thus removed
	Amendment of Section 3.0 Study Treatment: addition that participants could consume or abstain from coffee at their discretion following primary endpoint being met, end of study (6 months), or study withdrawal	Clarification that patients could consume or abstain at their discretion after their involvement in the trial was complete
	Miscellaneous: removal of day 1 study visit that was not undertaken, addition of heart failure exacerbation that was collected as an adverse event, removal of remaining references to coffee abstinence symptom assessment, clarification of wording, minor grammatical errors	Correction of several minor errors and clarification of wording throughout document

